All blood, urine, and lesion biopsy samples will be labeled with a codified number (will not contain any patient identifying information) and will be immediately transported to [name] laboratory (Sir Charles Tupper Medical Building, 11F11) at Dalhousie University for storage. Fine needle aspiration of excised samples will be assessed for tumor genetic and epigeneitic profile (Figure 2). Blood and urine will be assessed for proteomic and metabolomic profiles, respectively (Figure 2).

A database containing patient IDs and codified numbers will be restricted to the office of [name] (11th floor, VG). This is a locked office, and the data will only be accessible to the investigators named on this application. This database for will contain patient IDs, and info on disease status, treatment/control, follow up visits, and sample analysis – only info pertinent to the outcome measures. All sample data will be assessed using codified descriptors and will contain no patient ID info. Once the RNA, proteomic, metabolomic and pathology data has been analyzed, unmasking treatment and control groups will be conducted at the VG office of [name], by the named investigators. If the data reaches statistically significance, the study will not accept any more patients, if not, a further 10 patients will be incorporated – to a maximum of 60 patients. Any publications of study results will be completed devoid of any information that could be used to identify patients included in the study.

All study participants will receive biannual assessments for 5 years after the initial intervention to assess disease progression, or the development of new melanoma, to compare between both treatment and control groups. There is no standardize test or measurable biomarker to assess established or lasting immunity. This aspect of the study is identical to the patient assessment conducted as per standard of care for melanoma patients. Again, any publications of study results will be completed devoid of any information that could be used to identify patients included in the study.

	Interleukin 2 Treatment Group				
Interleukin-2 Treatment Group		Placebo Treatment Group			

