Day 1 Clinical Visit -Area of skin suspected of cancer photographed. -IL-2 treatment administered -Blood sampled – 4 tablespoons (60 ml) -Urine Sampled – 3 to 4 tablespoons (50 ml)		Day 1 Clinical Visit -Area of skin suspected of cancer photographed. -Placebo administered -Blood sampled – 4 tablespoons (60 ml) -Urine Sampled – 3 to 4 tablespoons (50 ml)			
Day 8 Clinical Visit -IL-2 treatment administered		Day 8 Clinical Visit -Placebo administered			
Day 15 Clinical Visit -Area of skin suspected of cancer photographed. -Blood sampled – 4 tablespoons (60 ml) -Urine Sampled – 3 to 4 tablespoons (50 ml)		Day 15 Clinical Visit -Area of skin suspected of cancer photographed. -Blood sampled – 4 tablespoons (60 ml) -Urine Sampled – 3 to 4 tablespoons (50 ml)			
-Surgical excision		-Surgical excision			
Confirmed melanoma patients -Follow up every 6 months for 5 years					
	
 
-Area of skin suspected of cancer photographed.
 
-IL-2 treatment administered
 
-Blood sampled – 4 tablespoons (60 ml)
 
-Urine Sampled – 3 to 4 tablespoons (50 ml)
 
 Day 8 Clinical Visit 
 
-IL-2 treatment administered
 
 Day 15 Clinical Visit 
 
-Area of skin suspected of cancer photographed.
 
-Blood sampled – 4 tablespoons (60 ml)
 
-Urine Sampled – 3 to 4 tablespoons (50 ml)
 
 Surgical excision Confirmed	
 
-Area of skin suspected of cancer photographed.
 
-IL-2 treatment administered
 
-Blood sampled – 4 tablespoons (60 ml)
 
-Urine Sampled – 3 to 4 tablespoons (50 ml)
 
 Day 8 Clinical Visit 
 
-IL-2 treatment administered
 
 Day 15 Clinical Visit 
 
-Area of skin suspected of cancer photographed.
 
-Blood sampled – 4 tablespoons (60 ml)
 
-Urine Sampled – 3 to 4 tablespoons (50 ml)
 
 Surgical excision Confirmed mela			

		Clinical and	Sub-s	study	Procedures
	Interleukin-2/Placebo Treatment Group			Sub-Study Process/Procedures	
Clinical Trial Procedures		Day 1 Clinical Visit -Area of skin suspected of cancer photographed -IL-2/Placebo treatment administered -Blood sampled – 4 tablespoons (60 ml) -Urine Sampled – 3 to 4 tablespoons (50 ml)			Day 1 Clinical Visit -Blood sample – To be used in proteomic sub- study (study of protein levels found in blood) -Urine Sample – To be used in metabolomic sub- study (study of metabolites released in urine)

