		Day 8 Clinical Visit -IL-2 treatment administered			Day 8 Clinical Visit -Nothing collected for sub-study at this visit
		Day 15 Clinical Visit -Area of skin suspected of cancer photographed -Blood sampled – 4 tablespoons (60 ml) -Urine Sampled – 3 to 4 tablespoons (50 ml)			Day 15 Clinical Visit -Blood sample – To be used in proteomic sub- study (study of protein levels found in blood) -Urine Sample – To be used in metabolomic sub- study (study of metabolites released in urine)
Standard of Care		-Surgical excision			-Biopsy sample collected from tissue removed during excision – To be used in RNA analysis sub- study (study of genes that may be involved in cancer development and growth)
Standa		-Confirmed melanoma patients Follow up every 6 months for 5 years			

Figure 2 Clinical and Sub-study Procedures

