#### Analysis of Data

#### Outcome measure/study objectives:

Assessment of Number of Patients Needed to Obtain Significance [**Time Frame: 1 year**] – Data will be analyzed in order to achieve a statistically significant differentiation between treatment and control outcomes in study measures including tumor infiltrating lymphocytes (TILs) and circulating immunomodulators.

Assessment of Metastasis [**Time Frame: 5 years**] - All patients will receive assessments every 4 months for 2 years and then biannual assessments for years 3-5 after the initial intervention to assess disease metastasis in treatment and control groups. Both number of new metastases (integer value) and thickness (mm) will be measured as a part of this assessment.

Sub-Study Outcome Measure:

Assessment of RNA genetic profile **[Time Frame: 5 years]** - RNA analysis of excised tissue will be compared to unaffected patient tissue obtained from the clear margins of the excisional biopsy to assess genetic changes resulting from the melanoma and treatment/placebo injections. RNA analysis will occur at [name] laboratory (Sir Charles Tupper Medical Building, 11F11) at Dalhousie University.

Assessment of Systemic Immune Response: Proteomic Analysis [**Time Frame: 5 years**] - Proteomic analysis will be conducted on blood samples to assess systemic immune response to both treatment and control groups. Serum collected from patient blood samples will be used for proteomic analysis to assess protein expression, including circulating immunomodulators (cytokines and chemokines) before, and after, treatment. Proteomic analysis will occur at Dalhousie's Proteomics and Mass Spectrometric Core Facility located in the Life Sciences Research Institute. This study may serve to help develop diagnostic protocols and methods of assessing response to treatments.

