#### How will the data be analyzed:

All study practices and statistical methods are based on the International Conference on Harmonization (IHC) document "Statistical Principles for Clinical Trials." Data will be summarized by treatment group. Baseline characteristic, safety outputs and a total overall column will be included to summarize all subjects. For all baseline, demographic, safety and efficacy outputs data will be summarized by treatment group. In summary tables of continuous variables, the minimum and maximum statistics, the arithmetic mean and median, the 95% confidence interval, standard deviation, and standard error will be presented will to the same number of decimal places as the original data. In summary tables of categorical variables, counts and percentages will be used. The denominator for each percentage will be the number of subjects within the population treatment group unless otherwise specified. All hypothesis testing will be carried out at the 5% (2-sided) significance level unless otherwise specified. P-values will be rounded to three decimal places. P-values less than 0.001 will be reported as <0.001 in tables.

The treatment label for all tables, listings and figures will be:

Treatment	Label
2 treatment cycles of	IL-2
500,000 IU of IL-2 in 0.1	Treatment
mL	
0.1 mL of sterile saline	Placebo
(0.9% m/v)	
All Treatments	Total

Where that any of the statistical methods described herein prove unsuitable during analysis, more appropriate methods will be used. All changes in methodology will be documented in the clinical study report. Additional ad-hoc analyses may be conducted as deemed suitable.

Subject inclusion/exclusion criteria will be determined at baseline visit, and subjects who do not meet all criteria will not be entered into the study. Those subjects deemed eligible to participate will be allocated a 3-digit number at randomization prior to the initial treatment. If a subject is discontinued at any time after entering the study, the Investigator will ensure this does not affect the patient's standard of care. At the patients request all unused biological samples (blood, urine, and core biopsies) will be immediately destroyed. The reasons for withdrawal will be recorded on the CRF and will be included in the final report. Failure to complete both (2) treatment cycles will result in patient removal from the trial.

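### The plan is inconsistent on who enters the 5-year follow-up, how often they are seen and whether new melanoma is an outcome, and its removal rule conflicts with following everyone

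*Combined protocol and SAP*

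**What the plan says.** Four places describe the same 5-year follow-up.

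- Research Plan, follow-up paragraph: "All study participants will receive biannual assessments for 5 years after the initial intervention", with the purpose "to assess disease progression, or the development of new melanoma, to compare between both treatment and control groups". The paragraph adds that this part of the study is "identical to the patient assessment conducted as per standard of care for melanoma patients".
- Outcome measure/study objectives, Assessment of Metastasis: "All patients will receive assessments every 4 months for 2 years and then biannual assessments for years 3-5". On the measures: "Both number of new metastases (integer value) and thickness (mm) will be measured as a part of this assessment".
- Figure 1 (treatment and placebo flow chart): "Confirmed melanoma patients -Follow up every 6 months for 5 years".
- Figure 2 (clinical and sub-study procedures), in the standard-of-care block: "Confirmed melanoma patients Follow up every 6 months for 5 years".

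The section on how the data will be analysed adds: "Failure to complete both (2) treatment cycles will result in patient removal from the trial".

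Nothing in the document says which statement governs.

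**The concern.** Patients are randomised on clinical suspicion and injected on Days 1 and 8. Histology comes from the Day 15 biopsy. If staff work from the figures, entry to the 5-year cohort is decided by a result obtained after randomisation and treatment, and patients with benign lesions have no study visits. Yet the section on proactive treatment suggests that IL-2 may help the immune system respond to melanoma cells that arise later. Patients with benign lesions carry information on that claim.

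The removal rule is a second way to lose randomised patients for something that happens after randomisation. It also sits badly with a promise to follow every participant.

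New melanoma is to be compared between arms according to the Research Plan, but it is not among the listed outcomes. It could therefore be collected and reported, or not, at discretion.

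**Working it through.** **Side by side**

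| Place | Who | When | What |
|---|---|---|---|
| Research Plan, follow-up paragraph | all participants | 6-monthly, 5 years | progression or new melanoma |
| Assessment of Metastasis | all patients | 4-monthly in years 1-2, then 6-monthly | metastasis: count and thickness |
| Figure 1 | confirmed melanoma | 6-monthly, 5 years | not stated |
| Figure 2 | confirmed melanoma | 6-monthly, 5 years | not stated |

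**Schedule.** Research Plan and figures: 5 × 2 = 10 visits (months 6, 12, 18, ..., 60). Assessment of Metastasis: 2 × 3 + 3 × 2 = 12 visits (months 4, 8, 12, 16, 20, 24, then 30 to 60 by sixes). Eight time points are shared. Months 6 and 18 occur only in the first schedule; months 4, 8, 16 and 20 only in the second. The conflict is confined to years 1-2, where the mean detection lag (half the interval) is 3 against 2 months. Reading biannual as once in two years does not remove it, because both figures say 6-monthly.

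**Who is followed.** The documents give no melanoma share; assume 30-80%. At 60 patients, benign cases number 60 × 0.2 = 12 to 60 × 0.7 = 42 (4 to 14 at 20 patients). With an assumed 5-year new-melanoma risk of 2-10% in every patient, the new melanomas falling outside scheduled follow-up number 12 × 0.02 = 0.24 to 42 × 0.10 = 4.2. That range is wide because none of its inputs is in the documents.

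**Removal rule.** Assume that 5-10% do not complete both injections: 60 × 0.05 = 3 to 60 × 0.10 = 6, or 1 to 2 of 20.

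**What following everyone does to the metastasis comparison.** Background Information gives 5-15% of melanoma patients progressing to stage IV, with no time horizon. The calculation takes half of patients as melanoma (assumed), 60 patients, complete prevention on IL-2 (a best case), Fisher's exact test at two-sided 5%, and patients with at least one metastasis as the events.

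- All randomised, 30 v 30: 0 v 5 gives p = 0.052 and 0 v 6 gives p = 0.024, so 6 placebo events are needed.
- Melanoma subset, 15 v 15: 0 v 5 gives p = 0.042, so 5 are needed.
- Rate 15%: diluted to 0.5 × 15% = 7.5% of all randomised. P(X ≥ 6 | 30, 0.075) = 2.2%, against P(X ≥ 5 | 15, 0.15) = 6.2% in the subset.
- Rate 30% (assumed): diluted to 15%. Power is 29% against 48%.
- Rate 40% (assumed): diluted to 20%. Power is 57% against 78%.
- Rate 5%: below 1% either way.

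**The case against.** The strongest reply is that the prose is explicit twice and should govern. The Figure 2 line stands in a standard-of-care block and may only mark what is routine. That is a reasonable reading, so the harm is conditional on the figures being used. But Figure 1, as far as it can be read, has no such label, and the Research Plan itself ties these visits to the routine care of melanoma patients. Site staff could fairly follow either.

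On the removal rule, it can be said that a removed patient is no longer a participant, so there is no strict contradiction. The loss of randomised patients remains on that reading.

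It can also be said that every version applies equally to both arms, that the enrolment decision rests on RNA, proteomic, metabolomic and pathology data and not on 5-year events, and that this is a pilot. All of that stands, and it limits the weight of the point.

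A reader might go further in five ways that the documents do not support:

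- *That the two statements of the event contradict each other.* Progression includes metastasis, so they largely overlap. The gap is new melanoma.
- *That the two compensated extra visits leave no room for following benign cases.* Those visits most naturally belong to the treatment phase, and a payment clause is not a visit schedule.
- *That new melanomas in benign cases could never be recovered.* Nothing rules out learning of them by another route.
- *That power for metastasis is very low whatever is done.* It depends on the rate. The 5-15% figure is progression to stage IV, and the two studies cited for it have titles about thin melanoma, whereas this trial enrols nodular, polypoid, bleeding or ulcerated lesions.
- *That selection by histology, or by completing both injections, biases the comparison between arms.* That would need IL-2 to change the diagnosis or the chance of completing. The protocol anticipates no specific change in the lesion over so short a period and gives no completion data by arm.

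**Conclusion.** The inconsistency is real and should be corrected. In order of weight:

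1. Who is followed: all randomised patients, or only those with melanoma confirmed on Day 15.
2. The removal of non-completers, which conflicts with following all participants.
3. New melanoma, which is compared in one place and not listed as an outcome in the other.
4. The schedule, which is minor.

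The sizes of 12 to 42 patients unfollowed and 3 to 6 removed, of 60, rest on assumed melanoma shares and completion rates. The first also requires that the figures be followed. The consequence is incomplete 5-year data on randomised patients, not a demonstrated bias and not an effect on the enrolment decision. The contradictions in the text need no assumption.

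**What to change.** - Change the follow-up line in Figures 1 and 2 to all randomised patients, whatever the Day 15 histology.
- State one schedule for both arms. Either is acceptable; choosing 6-monthly means editing the Assessment of Metastasis text only.
- Keep metastasis as the 5-year outcome, in line with the Hypothesis section, and list new primary melanoma as a separate named outcome.
- Amend the removal rule: a patient who does not complete both injections stops treatment but stays in follow-up and analysis unless consent is withdrawn, as the consent section already allows.
- Report all randomised patients, with the confirmed-melanoma subset as supporting, and describe the 5-year comparison as descriptive at pilot size.

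The cost is mainly the visits for benign cases, which the prose already promises. If half are benign (assumed), that is 30 × 10 = 300 to 30 × 12 = 360 visits at 60 patients, or 100 to 120 at 20. If the $25 visit payment were extended to them (also assumed), it comes to $7,500-9,000, or $2,500-3,000 at 20. The other cost is dilution: patients with benign lesions lower the metastasis rate in the all-randomised comparison, which is why the melanoma subset is kept alongside it.

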#### Analysis of Data

#### Outcome measure/study objectives:

Assessment of Number of Patients Needed to Obtain Significance [**Time Frame: 1 year**] – Data will be analyzed in order to achieve a statistically significant differentiation between treatment and control outcomes in study measures including tumor infiltrating lymphocytes (TILs) and circulating immunomodulators.

Assessment of Metastasis [**Time Frame: 5 years**] - All patients will receive assessments every 4 months for 2 years and then biannual assessments for years 3-5 after the initial intervention to assess disease metastasis in treatment and control groups. Both number of new metastases (integer value) and thickness (mm) will be measured as a part of this assessment.

Sub-Study Outcome Measure:

Assessment of RNA genetic profile **[Time Frame: 5 years]** - RNA analysis of excised tissue will be compared to unaffected patient tissue obtained from the clear margins of the excisional biopsy to assess genetic changes resulting from the melanoma and treatment/placebo injections. RNA analysis will occur at [name] laboratory (Sir Charles Tupper Medical Building, 11F11) at Dalhousie University.

Assessment of Systemic Immune Response: Proteomic Analysis [**Time Frame: 5 years**] - Proteomic analysis will be conducted on blood samples to assess systemic immune response to both treatment and control groups. Serum collected from patient blood samples will be used for proteomic analysis to assess protein expression, including circulating immunomodulators (cytokines and chemokines) before, and after, treatment. Proteomic analysis will occur at Dalhousie's Proteomics and Mass Spectrometric Core Facility located in the Life Sciences Research Institute. This study may serve to help develop diagnostic protocols and methods of assessing response to treatments.

Assessment of Systemic Immune Response: Metabolomic Analysis [**Time Frame: 5 years**] - Metabolomic analysis will be conducted on urine samples to assess systemic immune response to both treatment and control groups. All tumor and tissue produce by products in waste that are excreted by the kidneys. Urine samples can be evaluated using techniques, such as Mass Spectrometric, to determine if biological compounds can be identified in association with the presence of a malignant process that would not be produced by normal tissue. Metabolome analysis will occur at Dalhousie's Proteomics and Mass Spectrometric Core Facility located in the Life Sciences Research Institute. This study may serve to help develop diagnostic protocols and methods of assessing response to treatments.

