#### Hypothesis:

*Hypothesis*: Pre-treatment with IL-2 in patients with highly suspicious pigmented lesions will reduce the incidence of metastatic melanoma compared to the PBS placebo group by initiating an adaptive immune response to native melanoma protein and peptide. *Major Aims*:

- 1) To conduct a pilot study to assess the number of patients needed to analyze in order to achieve a statistically significant differentiation between treatment and control outcomes in study measures including tumor infiltrating lymphocytes (TILs) and circulating immunomodulators.
- 2) To assess the efficacy of intralesional pre-treatment of IL-2 on highly suspicious lesions in generating an adaptive immune response and preventing melanoma metastasis.
- 3) Sub-study To assess if there a difference in specific immune modulators in patients receiving IL-2 pre-treatment compared to patients receiving a placebo.

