This study is a randomized, controlled, double-blind study. Patients with highly suspicious pigmented lesions will be randomly assigned by an algorithm to one of two groups: 1) treatment group patients will be treated intralesionally with IL-2 (Proleukin (Aldesleukin), Novartis Pharmaceuticals Canada Inc.) at a dose of 500,000 International Units (IU) (0.1ml) for 2 treatment cycles 1 week apart (Day 1 and Day 8) Figure 1; 2) control group patients will be treated intralesionally with sterilized sodium chloride (0.9%, m/v) (0.1ml) Figure 1. Randomization will be done at the pharmacy for each patient (generated by a Random Block algorithm). IL-2 (Proleukin) will be obtained from the Provincial Drug Distribution Program by the pharmacy, paid for by [name] research services account (please see budget attached). The pharmacy will prepare either IL-2 treatment (supplied as 1 x 0.8ml (4 million units) or injectable placebo (0.9% sodium chloride) supplied as 0.8ml). The syringes will be prepared by following aseptic technique in a biohazard hood. A 22-million unit vial of IL-2 will be reconstituted with 1.2ml of sterile water for injection and mixed gently. After drawing up 3.2ml of 5% dextrose in water and transferring to the IL-2 vial, the resulting concentration will be 5 million units/ml. 0.8ml of the IL-2 solution will then be drawn into a 3ml syringe. Expiry time of the reconstituted solutions is 48 hours at 4C. The pharmacy will assign a codified ID which will be provided along with the syringe with the patient name labeled as "Interleukin-2/Placebo" (thus blinding study to clinician and patient). As a pilot study, the principle of the design is to test the feasibility of proceeding to a larger and more expensive trial following the methodology and protocol proposed. As such there will be a minimum of 20 (10 treatment, 10 placebo) participants (up to a maximum of 60). It is estimated that statistical significance will be reached with 20 patients, however it is not reached after 20 patients, an additional 10 (5 treatment, 5 control) patients will be enrolled. If significance is still not reached after 30 patients, an additional 10 patients will be enrolled and so on up to a maximum of 60 patients. If after 60 patients, significance is not achieved then further recruitment under the current protocol would not be logical and therefore the methodology would need to be revised or study discontinued.

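### Aim 1 asks how many patients are needed, but the plan's only route to a number is the cohort size at which p<0.05 first appears, a chance stopping point that is too small unless the true effect is about 1.3 SD or more

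*Combined protocol and SAP*

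**What the plan says.** All places are in the combined protocol and SAP.

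- **Hypothesis, Major Aims.** Aim 1 is "To conduct a pilot study to assess the number of patients needed to analyze in order to achieve a statistically significant differentiation" between the arms, on TILs and circulating immunomodulators.
- **Analysis of Data, Outcome measure/study objectives.** The first outcome is titled as an assessment of the number of patients needed for significance. Its method reads: "Data will be analyzed in order to achieve a statistically significant differentiation between treatment and control outcomes in study measures including tumor infiltrating lymphocytes".
- **Research Plan, size and extension.** The study has a "minimum of 20 (10 treatment, 10 placebo) participants (up to a maximum of 60". The basis for the first figure is an assertion: "It is estimated that statistical significance will be reached with 20 patients". Ten more patients follow if it is not reached, and then: "If significance is still not reached after 30 patients, an additional 10 patients will be enrolled and so on", to a ceiling of 60. If significance is still missing at 60, the methodology is to be revised or the study discontinued, and no number results.
- **Research Plan, unmasking.** "If the data reaches statistically significance, the study will not accept any more patients".
- **How will the data be analyzed.** "All hypothesis testing will be carried out at the 5% (2-sided) significance level unless otherwise specified". Means, SDs, standard errors and 95% confidence intervals are listed as table summaries for continuous variables, without any link to Aim 1.
- **Research Plan, purpose.** "As a pilot study, the principle of the design is to test the feasibility of proceeding to a larger and more expensive trial".

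No section gives a target difference, an SD, a power, a named test for TILs or a sample-size formula.

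**The concern.** The number of patients needed is a planning quantity. It follows from a difference worth detecting, the variability of the measure, the significance level and the power. The cohort size at the first significant look is something else: a random stopping time. Here it can only be 20, 30, 40, 50, 60 or not reached. It leans towards small values, because enrolment ends on the first favourable fluctuation. For the same reason the difference seen at that stop is exaggerated, so putting it into a formula afterwards does not repair the answer.

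This is separate from the type I error of repeated looks. Adjusting the significance level would control false positives, but it would not turn a stopping size into an estimate of the size a trial needs. At stake is whether the first-listed aim and outcome get a usable answer.

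**Working it through.** **Inputs from the documents.** Looks at 20, 30, 40, 50 and 60 patients, 1:1 at the first two looks (Research Plan); two-sided 5% at every test (How will the data be analyzed); stop at the first significant result (Research Plan).

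**Assumptions, because the documents are silent.** One normally distributed measure, equal variances, complete data, 1:1 allocation at all looks, two-sample t-test, true standardized difference d from 0 to 2 SD, power 80% or 90%.

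**Step 1: the plan's own figure.** The 20 patients cannot be reproduced, since no effect, SD, power or test is given. Solving backwards with the t-test, 10 per arm gives 80% power at d = 1.33 and 90% power at d = 1.53. A result at 10 per arm is significant only if the observed difference is at least 2.101 × √(2/10) = 0.94 SD.

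**Step 2: stopping size against size needed.** Simulation of 200,000 trials per effect, stopping at the first p<0.05. Size needed is the total from the t-test power function.

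| True d | Stop at 20 | Never significant by 60 | Median stop, if stopped | Needed, 80% power | Needed, 90% power |
|---|---|---|---|---|---|
| 0 | 5% | 87% | 30 | none exists | none exists |
| 0.5 | 18.5% | 43% | 30 | 128 | 172 |
| 0.8 | 39.5% | 10% | 30 | 52 | 68 |
| 1.0 | 56% | 2% | 20 | 34 | 46 |
| 1.33 | 80% | 0.1% | 20 | 20 | 26 |
| 1.5 | 89% | 0% | 20 | 18 | 22 |

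- With no effect, about 13% of runs return a number.
- At d = 0.5 every stop is at or below half of 128, and a new 30-patient trial has 26% power.
- At d = 0.8 the stops spread over 20, 30, 40, 50 and 60 in about 39.5%, 21%, 14%, 9% and 6% of runs. Of the runs that stop, 93% do so below 52. A new 20-patient trial has 39.5% power.
- At d = 1.0, 80% of the runs that stop do so below 34.
- At d = 1.33 the usual stop of 20 equals the 80%-power size but falls short of the 26 for 90%.

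**Step 3: the observed effect at the stop.** In runs that stop at 20, the mean observed difference is 1.32 SD when the truth is 0.8 and 1.22 SD when the truth is 0.5. Planning from 1.32 SD gives 2 × (1.96 + 0.84)² / 1.32² = 9.0 per arm (18 patients) by the normal formula. The t-based calculation gives about 10 per arm (20 patients). The size needed at the true 0.8 SD is 52.

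**Step 4: is this only multiplicity?** With a constant boundary holding about 5% overall (nominal p of about 0.018 per look) and d = 0.8, the stops still scatter: 24%, 19%, 16%, 12% and 9%, with 20% not reached. The mean effect at a 20-patient stop rises to 1.50 SD. Adjusting the level does not answer Aim 1.

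**Step 5: would the SD be a safe input?** Stopping on a t-test favours runs with a low SD. In runs stopping at 20, the mean pooled SD is 0.93 (d = 0.8) and 0.91 (d = 0.5), against an expected 0.99 without selection and a true value of 1. That is roughly 6–9% low. A sample size scales with the variance. The mean variance in those runs is 0.895 and 0.849, so N is 11% and 15% short; squaring the mean SDs gives 13% and 17%.

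**The case against.** **The link is inferred.** Nothing in the documents says that the stopping size will be reported as the answer to Aim 1. The Research Plan gives an enrolment rule, and the outcome text says only that data will be analysed. The planned tables include SDs and confidence intervals, and ad hoc analyses are allowed, so a proper calculation could be made afterwards. This stands as a limit on the wording. It does not remove the gap, because no such calculation is planned and the enrolment rule is the only stated procedure that produces a number.

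**The answer need not be far too small.** A reader might infer that it usually is. The documents give no effect size, so this cannot be said without a condition. If the true effect is the 1.33 SD that 20 patients imply at 80% power, the stop is about right, and at 1.5 SD it is slightly more than needed. This stands in full. However, that effect is only implied by an unsupported figure, so it cannot be presumed either.

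**Harm to the larger trial.** A reader might also infer that the later trial will be underpowered. The documents speak of the feasibility of proceeding to a larger trial and do not say that this number or effect will set its size. The harm is possible, not stated. Nor is Aim 1 clearly the main objective: the Research Plan says the study is primarily about whether tumor-specific immunity can be generated.

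**Conclusion.** The point holds in a conditional form. Aim 1 and the first outcome are a sample-size question with no stated method of estimation. The one procedure that yields a number gives a chance stopping size without a stated power, or no number at all. That size is typically too small unless the true effect is very large, about 1.3 SD or more at 80% power. The effect observed at an early stop should not be used for planning; if it were, a later trial could be underpowered.

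The size of the problem rests on the assumptions listed above, above all the true effect and a continuous TIL measure. The documents say only that the pathologist reports the extent of TILs and give no scale. The documents do not support a claim that the pilot is bound to give a wrong answer, or that the next trial will fail because of it. This should be fixed before the Aim 1 result is reported or used.

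**What to change.** 1. Redefine the Aim 1 outcome as a sample-size calculation for one named TIL measure on a stated scale.
2. Base it on the pooled within-arm SD with its 95% confidence interval, or on the control-arm proportion with its interval if TILs are graded in categories.
3. State the power (for example 80% and 90%) and use a difference chosen on clinical grounds, not the observed one.
4. Report N as the range implied by the interval. The 95% limits for an SD are 0.76 to 1.48 times the estimate at 20 patients and 0.85 to 1.22 times at 60. Since N scales with the square, a central answer of 52 becomes about 30 to 114 (52 × 0.58 to 52 × 2.19) and about 37 to 77 (52 × 0.72 to 52 × 1.49).
5. State that the cohort size at first significance is not the number of patients needed.
6. Either do not let significance end enrolment for this estimate, or state that an SD from an early significant stop is biased low by the amounts in Step 5 and plan from the upper part of its interval.

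**Cost.** Rewording of one aim and one outcome, and a short calculation. No extra visits or samples are needed. No extra patients are needed either, unless the first option in item 6 is taken, which can lengthen enrolment within the existing maximum of 60. The reported number will usually be larger and will come as a range.
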